#### 14.1.3.2.4 Time to treatment failure

This endpoint is often appropriate in studies of advanced disease where early discontinuation is typically related to intolerance of the study drug. In some protocols, time to treatment failure may be considered as a sensitivity analysis for time to progression. The list of discontinuation reasons to be considered or not as treatment failure may be adapted according to the specificities of the study or the disease.

**Time to treatment failure (TTF)** is the time from date of randomization/start of treatment to the earliest of date of progression, date of death due to any cause, or date of discontinuation due to reasons other than ‘Protocol violation’ or ‘Administrative problems’. The time to treatment failure for patients who did not experience treatment failure will be censored at last adequate tumor assessment.

#### 14.1.3.2.5 Duration of response

The analysis of the following variables should be performed with much caution when restricted to responders since treatment bias could have been introduced. There have been reports where a treatment with a significantly higher response rate had a significantly shorter duration of response but where this probably primarily reflected selection bias which is explained as follows: It is postulated that there are two groups of patients: a good risk group and a poor risk group. Good risk patients tend to get into response readily (and relatively quickly) and tend to remain in response after they have a response. Poor risk patients tend to be difficult to achieve a response, may have a longer time to respond, and tend to relapse quickly when they do respond. Potent agents induce a response in both good risk and poor risk patients. Less potent agents induce a response mainly in good risk patients only. This is described in more detail by [Morgan \(1988\)](#).

It is recommended that an analysis of all patients (both responders and non-responders) be performed whether or not a “responders only” descriptive analysis is presented. An analysis of responders should only be performed to provide descriptive statistics and even then interpreted with caution by evaluating the results in the context of the observed response rates... If an inferential comparison between treatments is required this should only be performed on all patients (i.e. not restricting to “responders” only) using appropriate statistical methods such as the techniques described in [Ellis et al \(2008\)](#). It should also be stated in the protocol if duration of response is to be calculated in addition for unconfirmed response.

For summary statistics on “responders” only the following definitions are appropriate. (Specific definitions for an all-patient analysis of these endpoints are not appropriate since the status of patients throughout the study is usually taken into account in the analysis).

**Duration of overall response (CR or PR):** For patients with a CR or PR (which may have to be confirmed the start date is the date of first documented response (CR or PR) and the end date and censoring is defined the same as that for time to progression.

The following two durations might be calculated in addition for a large Phase III study in which a reasonable number of responders is seen.

**Duration of overall complete response (CR):** For patients with a CR (which may have to be confirmed) the start date is the date of first documented CR and the end date and censoring is defined the same as that for time to progression.

**Duration of stable disease (CR/PR/SD):** For patients with a CR or PR (which may have to be confirmed) or SD the start and end date as well as censoring is defined the same as that for time to progression.

#### 14.1.3.2.6 Time to response

**Time to overall response (CR or PR)** is the time between date of randomization/start of treatment until first documented response (CR or PR). The response may need to be confirmed depending on the type of study and its importance. Where the response needs to be confirmed then time to response is the time to the first CR or PR observed.

Although an analysis on the full population is preferred a descriptive analysis may be performed on the “responders” subset only, in which case the results should be interpreted with caution and in the context of the overall response rates, since the same kind of selection bias may be introduced as described for duration of response in [Section 14.1.3.2.5](#). It is recommended that an analysis of all patients (both responders and non-responders) be performed whether or not a “responders only” descriptive analysis is presented. Where an inferential statistical comparison is required, then all patients should definitely be included in the analysis to ensure the statistical test is valid. For analysis including all patients, patients who did not achieve a response (which may have to be a confirmed response) will be censored using one of the following options.

- at maximum follow-up (i.e. FPFV to LPLV used for the analysis) for patients who had a PFS event (i.e. progressed or died due to any cause). In this case the PFS event is the worst possible outcome as it means the patient cannot subsequently respond. Since the statistical analysis usually makes use of the ranking of times to response it is sufficient to assign the worst possible censoring time which could be observed in the study which is equal to the maximum follow-up time (i.e. time from FPFV to LPLV)
- at last adequate tumor assessment date otherwise. In this case patients have not yet progressed so they theoretically still have a chance of responding

**Time to overall complete response (CR)** is the time between dates of randomization/start of treatment until first documented CR. Similar analysis considerations including (if appropriate) censoring rules apply for this endpoint described for the time to overall response endpoint.

#### 14.1.3.2.7 Definition of start and end dates for time to event variables

##### **Assessment date**

For each assessment (i.e. evaluation number), the **assessment date** is calculated as the latest of all measurement dates (e.g. X-ray, CT-scan) if the overall lesion response at that assessment is CR/PR/SD/UNK. Otherwise - if overall lesion response is progression - the assessment date is calculated as the earliest date of all measurement dates at that evaluation number.

## Start dates

For all “time to event” variables, other than duration of response, the randomization/ date of treatment start will be used as the start date.

For the calculation of duration of response the following start date should be used:

- Date of first documented response is the assessment date of the first overall lesion response of CR (for duration of overall complete response) or CR / PR (for duration of overall response) respectively, when this status is later confirmed.

## End dates

The end dates which are used to calculate ‘time to event’ variables are defined as follows:

- Date of death (during treatment as recorded on the treatment completion page or during follow-up as recorded on the study evaluation completion page or the survival follow-up page).
- Date of progression is the first assessment date at which the overall lesion response was recorded as progressive disease.
- Date of last adequate tumor assessment is the date the last tumor assessment with overall lesion response of CR, PR or SD which was made before an event or a censoring reason occurred. In this case the last tumor evaluation date at that assessment is used. If no post-baseline assessments are available (before an event or a censoring reason occurred) the date of randomization/start of treatment is used.
- Date of next scheduled assessment is the date of the last adequate tumor assessment plus the protocol specified time interval for assessments. This date may be used if back-dating is considered when the event occurred beyond the acceptable time window for the next tumor assessment as per protocol (see [Section 14.1.3.2.8](#)).

**Example** (if protocol defined schedule of assessments is 3 months): tumor assessments at baseline - 3 months - 6 months - missing - missing - PD. Date of next scheduled assessment would then correspond to 9 months.

- Date of discontinuation is the date of the end of treatment visit.
- Date of last contact is defined as the last date the patient was known to be alive. This corresponds to the latest date for either the visit date, lab sample date or tumor assessment date. If available, the last known date patient alive from the survival follow-up page is used. If no survival follow-up is available, the date of discontinuation is used as last contact date.
- Date of secondary anti-cancer therapy is defined as the start date of any additional (secondary) antineoplastic therapy or surgery.

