### 7.1.4 Discontinuation of study treatment

Patients may voluntarily discontinue from the study treatment for any reason at any time. If a patient decides to discontinue from the study treatment, the investigator must make every effort (e.g. telephone, e-mail, letter) to determine the primary reason for this decision and record this information in the patient's chart and on the appropriate CRF pages. They may be considered withdrawn if they state an intention to withdraw, fail to return for visits, or become lost to follow-up for any other reason.

The investigator should discontinue study treatment for a given patient if, on balance, he/she believes that continuation would be detrimental to the patient's well-being.

Study treatment may be discontinued if any of the following occur:

- Adverse event
- Lost to follow-up

- Physician's decision
- Progressive disease per irRC (not per RECIST)
- Study terminated by the sponsor
- Subject/guardian decision
- Protocol deviation
- Technical problems

Study treatment must be discontinued if any of the following occur:

- Death
- Pregnancy

At the time patients discontinue study treatment, a visit should be scheduled as soon as possible, and within 14 days of the last dose of study drug or within 14 days of the decision to permanently discontinue study treatment, at which time all of the assessments listed for the EOT visit will be performed (Table 7-1). If the decision to withdraw the patient occurs at a regularly scheduled visit, that visit may become the EOT visit rather than having the patient return for an additional visit. An End of Treatment Phase Disposition CRF page should be completed, giving the date and reason for stopping the study treatment. End of treatment/Premature withdrawal visit is not considered as the end of the study.

Patients who discontinue study treatment should NOT be considered withdrawn from the study. They should return for the assessments indicated in Section 7.1.6. If they fail to return for these assessments for unknown reasons, every effort (e.g. telephone, email, letter) should be made to contact them as specified in Section 7.1.7. If a patient discontinues study treatment, but continues study assessments, the patient remains on study until such time as he/she completes protocol criteria for ending study assessments.

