### 7.1.6 Follow up period

All patients must have safety evaluations for 150 days after the last dose of study treatment. The evaluations can be done either by telephone call or visit for the 30-, 90-, and 150-day safety follow-up visits. Concomitant medications will be collected until the 30-day safety follow-up has been completed or the start of new antineoplastic therapy, whichever occurs first. If the 150-day safety evaluation is conducted by phone, samples do not need to be collected. Data collected should be added to the Adverse Events CRF, the antineoplastic therapies since discontinuation of study treatment CRF, the Concomitant Medications CRF, Biomarker blood sample CRF, and PK [REDACTED] CRFs. For PK [REDACTED] samples and Biomarker samples collection schedule is outlined in [Section 7.2.3](#) and [Section 7.2.4](#) respectively. For female patients of child bearing potential, pregnancy tests will be performed as outlined in [Section 7.2.2.5.7](#).

Patients who discontinue study treatment for any reason other than death, disease progression per irRC, clinical progression, lost to follow-up, consent withdrawal, start of new cancer therapy or study termination, also should return for tumor evaluation assessments and should not be considered withdrawn from the study until 80% of the patients in each disease group of the

phase II part have had progression of disease or discontinued the study for any reason. If patients refuse to return for these visits or are unable to do so, every effort should be made to contact them or a knowledgeable informant by telephone to determine if the patient had disease progression. Once the Follow up for Disease progression period ended, the End of Post treatment Phase disposition CRF should be completed.

Upon completion of the 150-day follow up or/and disease progression follow up, patients will be followed for survival every 3 months (can be done by telephone call) until death or until the end of the study is reached, unless they withdraw consent or are lost to follow-up.

Antineoplastic therapies since discontinuation of study drug will be collected during this follow-up period.

For patients who transfer to another clinical study or an alternative treatment option to continue provision of study treatment, as described in [Section 4.3](#), the follow-up for 150-day safety, disease progression and survival will not be performed.

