3.7.5.3 Association between biomarkers and clinical outcome

PD-L1 and potential predictors of efficacy

Associations of PD-L1 expression and efficacy outcome (e.g. ORR, DOR and DCR) will be assessed using various approaches, such as tabulations of ORR by PD-L1 expression status, Kaplan-Meier plots and estimates of PFS by PD-L1 expression status, and OS estimates by PD-L1 expression status.

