Missing death date

For cases when either day is missing or both month and day are missing for the date of death, the following imputation rules will be implemented:

- If only day is missing, then impute max [(1 mmm-yyyy), min (last contact date + 1, cutoff date)].
- If both day and month are missing, then impute max [(1 Jan-yyyy, min (last contact date + 1, cut-off date)].

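### The last-contact bullet in Protocol 14.1.3.2.7 contradicts itself, and its end-of-treatment fallback would censor some discontinued patients too early in any OS analysis that uses it

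*Protocol*

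**What the plan says.** The bullet on date of last contact (Protocol 14.1.3.2.7, End dates) opens by defining it as the final date on which the patient is documented alive, and explains: "This corresponds to the latest date for either the visit date, lab sample date or tumor assessment date". Two further sentences follow. The first is "If available, the last known date patient alive from the survival follow-up page is used". The second is "If no survival follow-up is available, the date of discontinuation is used as last contact date". An adjacent bullet fixes the meaning of that date: "Date of discontinuation is the date of the end of treatment visit".

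Protocol 7.1.4 places the end-of-treatment visit "within 14 days of the last dose of study drug or within 14 days of the decision to permanently discontinue study treatment". After it, Table 7-1 (footnote 4) and Section 7.1.6 require safety contacts at 30, 90 and 150 days after the last dose. Section 7.1.6 also requires continued scans for patients who stopped without progression, new cancer therapy or certain other reasons. Survival contacts come later: "Upon completion of the 150-day follow up or/and disease progression follow up, patients will be followed for survival every 3 months".

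Last contact matters in two visible places in the SAP. Section 3.7.5.3 lists "OS estimates by PD-L1 expression status" among its example analyses. Section 4.1.2 uses a last contact date to complete partial death dates, starting "If only day is missing, then impute max", without defining that date or citing the protocol.

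**The concern.** The first part of the bullet is the usual and correct rule. The last two sentences, read literally, cover every discontinued patient: the survival page if there is one, the end-of-treatment visit if there is not. On that reading the latest-date rule never operates for them. The schedule then guarantees a window in which a patient off treatment has documented later contacts but no survival page.

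If OS is censored at this date, follow-up is removed only from patients who are alive, while deaths in the same window still count at their true dates. Person-time at risk shrinks and events do not, so the hazard is overstated and the Kaplan-Meier curve is too low. If SAP 4.1.2 uses the same date, a partial death date could be placed before a contact at which the patient was alive. At the least, two programmers following this text could produce different OS curves.

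**Working it through.** The documents give no OS figure, OS assumption or count of affected patients, so there is no plan figure to reproduce. The check is date arithmetic plus an illustration on assumed inputs.

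**1. Who is affected.**
- Still on treatment: there is no end-of-treatment visit, so the fallback is undefined and the latest-date rule must apply. Nothing is lost.
- Off treatment with a survival page: the page date is used, so the fallback does not apply.
- Transferred to another study or treatment option (7.1.6): no follow-up takes place after end of treatment. Nothing is lost.
- Off treatment, no survival page, no contact after end of treatment: nothing is lost.
- Off treatment, no survival page, later safety contact or scan: known-alive time is lost.

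**2. Time lost per affected patient.** The last safety contact is 150 days after the last dose. With an end-of-treatment visit 0 to 14 days after the last dose, the loss is up to 150 - 14 = 136 to 150 - 0 = 150 days. Divided by 30.4375, that is 4.5 to 4.9 months. It is less if the visit is timed from a later decision to stop, and more if scans continue.

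**3. When it happens.** A primary CSR can be cut once all patients in an indication have discontinued or completed six cycles (Protocol Section 10). That is 6 x 28 = 168 days on Q4W and 6 x 21 = 126 days on Q3W. A patient who stopped within 150 days before that cut-off would normally have no survival page.

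**4. Illustrative size at an early cut-off.** Assumptions: exponential OS with median 6, 12 or 24 months, paired with time on treatment of median 2, 3 or 6 months; uniform accrual over 12 or 24 months; cut-off 168 days after the last entry; first survival page 150 + 90 = 240 days after end of treatment; 0% or 10% lost before any survival page; post-treatment scans not modelled; 200,000 simulated patients per setting. Cells give the percentage affected, then 12-month OS under the fallback and under latest contact, with the difference in points.

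| True median OS, accrual (months) | True 12-month OS | No loss | 10% lost |
|---|---|---|---|
| 6, 12 | 25.0% | 14.8%; 18.6 vs 21.9 (3.3) | 17.8%; 17.7 vs 21.9 (4.2) |
| 6, 24 | 25.0% | 7.4%; 22.2 vs 23.7 (1.5) | 11.1%; 21.4 vs 24.0 (2.6) |
| 12, 12 | 50.0% | 25.0%; 42.4 vs 47.1 (4.7) | 28.2%; 41.3 vs 47.0 (5.7) |
| 12, 24 | 50.0% | 12.9%; 46.9 vs 48.9 (2.0) | 17.5%; 45.9 vs 48.9 (3.0) |
| 24, 12 | 70.7% | 29.4%; 65.9 vs 69.1 (3.2) | 32.1%; 65.6 vs 69.3 (3.7) |
| 24, 24 | 70.7% | 17.4%; 68.8 vs 70.0 (1.2) | 21.9%; 68.3 vs 70.1 (1.8) |

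The fallback is lower in all 12 settings, by 1.2 to 5.7 points, with 7% to 32% of patients affected. Estimated median OS is lower by 0.3-0.7 months at a true median of 6 months (for example 5.2 vs 5.9) and by 0.6-1.6 months at a true median of 12 (9.6 vs 11.2). Latest contact is closer to the truth but does not remove all bias at an early cut-off.

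**5. Effect of maturity.** A similar simulation used 12-month accrual, OS median 6-18 months, treatment median 2-4 months, 15% of patients scanned after stopping, and no loss to follow-up. The understatement of 12-month OS was about 4-5.5 points with the cut-off 5.5 months after the last entry, about 0.5-1 point at 12 months, and about 0.1 point or less at 24 months. Patients lost before a first survival contact never acquire a survival page, so for them the effect does not fade.

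**6. Partial death dates, if SAP 4.1.2 means this date.** The rule takes the later of the first day of the known period and the earlier of (last contact + 1, cut-off). Suppose end of treatment was 10 January, a scan was done on 10 June, and death is recorded as June with no day. The fallback gives max(1 June, 11 January) = 1 June, nine days before the scan. Latest contact gives max(1 June, 11 June) = 11 June. With only the day missing, the floor at the first of the month keeps the error under one month. With day and month missing, the fallback gives max(1 January, 11 January) = 11 January, five months early.

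**The case against.** A reader might infer that the plan plainly orders follow-up to be truncated for every discontinued patient without a survival page, and that OS is therefore biased downward. The documents do not support that, for five reasons.

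- The same bullet contains the correct rule, and nothing says the last sentence overrides it. The fallback cannot work for patients still on treatment, so the latest-date rule must survive for some. This is a contradiction within the bullet.
- OS is not among the endpoints visible in Protocol Table 3-1 or SAP Table 1-1. The text between the PFS and time-to-progression definitions is redacted, so how OS is censored cannot be seen. The one visible OS output is an example in a biomarker section. ORR, PFS and DOR are not censored at last contact.
- Transferred patients and those with no later contact lose nothing. A responder scanned for a year is held at end of treatment only until the first survival contact.
- The SAP reviewed is for the final CSR and is dated 24 July 2020, about 28 months after the last enrolment on 22 March 2018 (the data cut-off is not shown). At that maturity, without loss to follow-up, the effect nearly disappears.
- SAP 4.1.2 does not say that its last contact date is the protocol's.

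All of these points stand and limit the scope. They do not remove the contradiction. No SAP text resolves it, and the irRC end-date list in SAP 4.2.4.2 has no last-contact rule at all. Followed as written, the fallback is a wrong rule for patients with later proof of life.

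**Conclusion.** The point holds as an internal contradiction with a conditional consequence. If the fallback is followed and OS is censored at last contact, OS is understated, because known-alive time is dropped while deaths are kept. The direction follows from the rules. The size rests on assumed survival, treatment duration, accrual and loss: roughly 1-6 points of 12-month OS at an early primary CSR cut-off, and close to nil at the final CSR apart from patients lost before their first survival contact. The true size cannot be computed from the documents.

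The visible reach is the OS estimates by PD-L1 status and any redacted OS analysis. Whether the comparison between PD-L1 groups is distorted, and in which direction, cannot be told from the documents. PFS and DOR could be touched only through partial death dates, if SAP 4.1.2 uses the same date, and probably in few patients. ORR is unaffected.

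**What to change.** Delete the end-of-treatment fallback. State the following in the protocol bullet, and repeat it in SAP 4.1.2 so that OS censoring and death-date imputation share one definition:

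*The date of last contact is the latest date on which the patient is known to be alive from any visit, 30-, 90- or 150-day safety contact (including by telephone), laboratory sample, tumour assessment or survival contact, capped at the data cut-off and at withdrawal of consent.*

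Telephone contacts should be named, because Protocol 7.1.6 allows them and a visit date may not cover them. The consent cap matches SAP 2.3.9, which excludes data collected after withdrawal. Transferred patients keep their end-of-treatment date, since that visit is their last contact.

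The cost is one sentence in each document and a small programming change, using dates the protocol already collects. If OS was shown in a primary CSR under the fallback, it should be rerun with this definition.
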